A DLT will be defined as any of the events described below occurring in a subject during the DLT window, unless clearly attributable to causes other than investigational product. The DLT window will start on day 1 and last for the duration of cycle 1. The CTCAE v5 will be used to assess toxicities/adverse events with the exception of CRS (see [Table 6-5](#) for grading of CRS).

DLT Evaluation

To be DLT evaluable, subjects must meet 1 of the following criteria during DLT evaluation period (cycle 1 day 1 to cycle 1 end of infusion):

- The subject experienced a DLT; OR
- The subject has received at least 70% of planned cumulative dose of AMG 330 and has not missed more than 1 dose of pembrolizumab; OR
- The subject did not experience a DLT and completed the DLT evaluation period

Events listed below are to be considered as DLTs and exceptions when occurring in a subject during the DLT window unless clearly attributable to causes other than AMG 330 and pembrolizumab treatment:

- Any treatment-related death.
- Grade 4 neutropenia lasting \geq 4 weeks from last day of cycle in absence of evidence of active AML. Note: grade 4 neutropenia maybe assessed retrospectively and outside of the DLT window
- Grade 3–4 non-hematologic toxicity not clearly resulting from the underlying leukemia EXCEPT:
 - Grade 3 fatigue, asthenia, fever, anorexia, or constipation
 - Grade 3 nausea, vomiting or diarrhea not requiring tube feeding, total parenteral nutrition, or requiring or prolonging hospitalization
 - Infection, bleeding, or other expected direct complication of cytopenias due to active underlying leukemia
 - Grade 3 infusion reaction, unless attributed to pembrolizumab, if successfully managed and which resolves within 72 hours
 - Grade 3 rash or pruritus
 - Grade 3 or 4 tumor lysis syndrome if it is successfully managed clinically and resolves within 7 days without end-organ damage.

Approved

- Grade 3 or 4 isolated analyte abnormalities (ie, those occurring without clinical consequence) that resolve, with or without intervention, to < grade 2 levels in < 72 hours will not be considered DLT.
- Grade 3 or 4 asymptomatic enzyme elevations including aspartate aminotransferase (AST), alanine aminotransferase (ALT) (without bilirubin elevation), gamma glutamyl transferase that resolve, with or without intervention, to ≤ grade 2 within 7 days will not be considered a DLT, unless attributed to pembrolizumab.

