- Isolated grade 3 elevation of amylase or lipase not associated with clinical or radiological evidence of pancreatitis
- Grade 3 endocrinopathy that is well controlled by hormone replacement
- CRS meeting any of the criteria listed below:
 - Grade 2 CRS that does not resolve, with or without intervention to grade 1 within 7 days will be considered a DLT
 - Grade 3 CRS that does not resolve, with or without intervention to ≤ grade 2 within 5 days, will be considered a DLT
 - Any grade 4 CRS
- Any grade 5 toxicity
- Receive less than 70% of the planned cumulative dose of AMG 330 or miss more than 1 dose of pembrolizumab during the first cycle due to investigational product(s) related toxicity that does not meet the DLT criteria listed above

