Dexamethasone (8 mg IV) should be administered within 1 hour prior to re-start and within 1 hour prior to each AMG 330 dose step(s). Dexamethasone is not required prior to the pembrolizumab administration unless it co-occurs with the AMG 330 step dose. In cases when administration of pembrolizumab co-occurs with AMG 330 step, pembrolizumab is administered first followed by dexamethasone followed by AMG 330. The subject should be hospitalized starting from re-start of infusion until 72 hours after the dose step. After each dose level increase, vital signs will be obtained as per the Schedule of Activities (see [Table 1-1](#), [Table 1-3](#), [Table 1-5](#)).

The number of days of exposure to both investigational products before and after an interruption should sum up to at least 70% of planned cumulative dose of AMG 330. In this case, the subject would still be DLT-evaluable. However, if the cycle was interrupted for more than 24 hours but less than 21 days, a new repeat cycle should be started and the interrupted cycle would not be evaluable for DLT, unless the event that lead to the interruption was a DLT.

Note: The end of infusion bone marrow assessment should be performed once it is confirmed that the cycle will not be resumed to assess treatment response. [REDACTED]

[REDACTED]

[REDACTED].

Permanent Discontinuation

A subject will permanently discontinue treatment with investigational product in the event of:

- Dose-limiting or other unmanageable toxicity. Exception: If a DLT occurs in a subject with a clear clinical benefit from treatment a restart at a lower dose can be considered if the toxicity has resolved and after consultation with the sponsor. This includes:
 - Grade 4 CRS
 - Grade 3 CRS occurring at the initial step dose for a cycle (ie, at the 10 µg/day)
 - Grade 2 or 3 CRS meeting any of the criteria listed below:
 - Grade 2 or 3 CRS that does not improve to ≤ grade 1 within 7 days
 - Grade 3 CRS that does not improve to ≤ grade 2 within 5 days
- Re-occurrence of the same grade 4 adverse event
- 3 infusion interruptions > 24 hours in cycle 1
- Disease progression as defined by 2017 European LeukemiaNet (ELN) criteria ([Döhner et al, 2017](#))
- Withdrawal of subject's consent to treatment
- Subject or investigator not compliant with the study protocol
- Occurrence or progression of a medical condition which in the opinion of the investigator should preclude further participation of the subject in the study

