3	Symptoms require and respond to aggressive intervention 
 • Oxygen requirement $\geq 40\%$, OR • Hypotension requiring high dose^b or multiple vasopressors, OR • Grade 3 organ toxicity or grade 4 transaminitis per CTCAE v5 criteria 	Admit to intensive care unit for close clinical and vital sign monitoring per institutional guidelines. Administer tocilizumab 8 mg/kg IV. Up to 3 additional doses of 8 mg/kg of tocilizumab can be given 8 hours apart, if needed. Administer dexamethasone (or equivalent) IV at a dose maximum of 3 doses of 8 mg (24 mg/day). The dose should then be reduced step-wise.	Immediately interrupt AMG 330 until event resolves to CRS grade ≤ 1 . Discontinue AMG 330 if there is no improvement to CRS \leq grade 2 within 5 days or CRS \leq grade 1 within 7 days. Permanently discontinue AMG 330 if CRS grade 3 occurs at the initial step dose (ie, at MTD1). Do not administer pembrolizumab until symptoms improve to CRS grade ≤ 1 If recurrent grade 3 CRS, permanently discontinue pembrolizumab.
4	Life-threatening symptoms 
 • Requirement for ventilator support OR • Grade 4 organ toxicity (excluding transaminitis) per CTCAE criteria 	Admit to intensive care unit for close clinical and vital sign monitoring per institutional guidelines. Administer dexamethasone (or equivalent) IV at a dose maximum of 3 doses of 8 mg (24 mg/day). Further corticosteroid use should be discussed with the Amgen medical monitor. Additionally, tocilizumab should be administered at a dose of 8 mg/kg. Up to 3 additional doses can be given 8 hours apart, if needed.	Immediately stop the infusion and permanently discontinue AMG 330 therapy and pembrolizumab therapy.

Page 2 of 2

CRS = cytokine release syndrome; CTCAE = Common Terminology Criteria for Adverse Events;

IV = intravenous; MTD = maximum tolerated dose

^a Revised grading system for cytokine release syndrome (Lee et al, 2014).^b High dose vasopressors (all doses are required for ≥ 3 hours): norepinephrine monotherapy ≥ 20 μ g/min; dopamine monotherapy ≥ 10 μ g/kg/min, phenylephrine monotherapy ≥ 200 μ g/min, epinephrine monotherapy ≥ 10 μ g/min; if on vasopressin, vasopressin + norepinephrine equivalent of ≥ 10 μ g/min; if on combination vasopressors (not vasopressin), norepinephrine equivalent of ≥ 20 μ g/min.^c Investigators may also consider additional therapy, based on clinical judgment.

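### The grade 3 CRS clause of the DLT definition lacks the 7-day limit that stops treatment, so a slowly resolving grade 3 event late in cycle 1 may go uncounted

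*Protocol*

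**What the plan says.** Three places in the protocol set time limits for CRS.

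- **DLT definition (Section 6.2.1).** Grade 3: "Grade 3 CRS that does not resolve, with or without intervention to" ≤ "grade 2 within 5 days, will be considered a DLT". Grade 2: "Grade 2 CRS that does not resolve, with or without intervention to grade 1 within 7 days will be considered a DLT". Any grade 4 CRS is also a DLT.
- **Permanent discontinuation (Section 6.2.2.1).** "Grade 2 or 3 CRS that does not improve to" ≤ grade 1 within 7 days is a reason to stop. So is grade 3 CRS that does not reach grade 2 or lower within 5 days. An exception follows the wording "If a DLT occurs in a subject with a clear clinical benefit from treatment a restart at a lower dose can be considered".
- **Table 6-5, grade 3 row (Section 6.8).** "Discontinue AMG 330 if there is no improvement to CRS" grade 2 or lower within 5 days, or grade 1 or lower within 7 days.

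Section 6.2.1 also has a catch-all DLT, for product-related toxicity that meets no other criterion: "Receive less than 70% of the planned cumulative dose of AMG 330 or miss more than 1 dose of pembrolizumab during the first cycle". One of the alternative routes to being DLT-evaluable mirrors it: "The subject has received at least 70% of planned cumulative dose of AMG 330 and has not missed more than 1 dose of pembrolizumab". SAP Section 5.4 leaves DLT classification to the investigator under protocol Section 6.2.1 and adds no CRS rule.

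**The concern.** The stopping rules hold three CRS duration limits: grade 2 to grade 1 in 7 days, grade 3 to grade 2 in 5 days, and grade 3 to grade 1 in 7 days. The DLT definition has the first two and lacks the third. Nothing says that the difference is intended.

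The grade 2 clause does not reliably fill the gap. Its clock has no stated start. Appendix 4 (Section 11.4) has an event whose grade changes recorded once, at its worst severity, so a grade 3 event that falls to grade 2 remains a grade 3 event on the CRF. Two sites could classify the same event differently.

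DLT incidence is a primary endpoint, reported on DLT-evaluable subjects. CRS is also a main risk of the combination: Section 2.3 warns that PD-1 blockade may lead to higher CRS grades.

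**Working it through.** **The plan's own figures.** None depends on this clause, but they reproduce. The chance of at least 1 DLT in 6 at a 25% rate is 1 − 0.75^6 = 0.822 (stated 82%). The chance of 3 or more DLTs in 10 at rates of 10, 20, 30, 40 and 50% is 0.070, 0.322, 0.617, 0.833 and 0.945 (stated 7, 32, 62, 83 and 95%).

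**Step 1: one event under each reading.** Take CRS at grade 3 on days 0–3, grade 2 on days 3–9, then grade 1.

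- Stopping rule: above grade 1 for 9 days, 9 > 7, so AMG 330 is discontinued.
- Grade 3 DLT clause: grade 2 reached at day 3, 3 ≤ 5, not met.
- Grade 2 DLT clause, clock from CRS onset: 9 > 7, DLT.
- Grade 2 DLT clause, clock from the fall to grade 2: 9 − 3 = 6 ≤ 7, not a DLT.
- Grade 2 DLT clause, read as not covering an event recorded as grade 3: not a DLT.

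A milder event at grade 2 for 8 days is a DLT (8 > 7). With the clock restarted at grade 2, an event peaking at grade 3 can stay at grade 2 or higher for up to 5 + 7 = 12 days without meeting a CRS clause.

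**Step 2: what the 70% clause catches.** Step lengths in days come from Tables 4-1 and 4-3. Cohort 1: 3, 4, 14, 7, 14, 7, 14, 14 (77 days). Cohort 2: 3, 4, 7, 7, 7, 7, 7, 14 (56 days). Doses are redacted, so I assume a constant ratio r between the 8 steps, with the dose at step i proportional to r^i. The 70% day is the first day on which cumulative dose divided by total planned dose is at least 0.70. A permanent stop for an event starting after that day escapes the dose limb.

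| r | Cohort 1: share before last step | 70% day | Days left of 77 | Cohort 2: share before last step | 70% day | Days left of 56 |
|---|---|---|---|---|---|---|
| 1.25 | 0.696 | 64 | 13 | 0.594 | 46 | 10 |
| 1.5 | 0.592 | 67 | 10 | 0.475 | 48 | 8 |
| 2 | 0.450 | 70 | 7 | 0.329 | 50 | 6 |
| 3 | 0.304 | 71 | 6 | 0.200 | 51 | 5 |

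The last step starts on day 64 in cohort 1 and day 43 in cohort 2. In every row less than 70% of the dose precedes it, so every dose increase comes before the 70% point. The uncovered days are 6/77 = 8% to 13/77 = 17% of infusion days in cohort 1, and 5/56 = 9% to 10/56 = 18% in cohort 2.

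**Step 3: the pembrolizumab limb.** Doses fall on days 15, 36 and 57 in cohort 1 and days 1, 22 and 43 in cohort 2, all before the 70% days above. Table 4-1 also lists day 78, in the infusion-free period. A late event can therefore cause at most one missed dose by itself, and the clause needs more than one.

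**Step 4: the day-28 rule.** By day 28 a cohort 1 subject has had at most 28/77 = 36% of planned dose (the equal-dose limit; less with escalation). A permanent stop by then falls below 70% and counts as a DLT.

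**The case against.** Several points against this have weight.

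- **Clock from onset.** One event has one onset date, and no text starts a new clock at downgrade. On that reading the example is a DLT and the gap closes. This stands as a condition on the point, but the protocol does not state the reading.
- **General grade 3–4 non-hematologic clause.** CRS is not among its exceptions, so read literally it counts every grade 3 CRS. That would leave the specific 5-day clause without effect, so the CRS criteria are the natural governing rule.
- **Evaluability.** Section 6.2.2.1 makes a cycle interrupted for more than 24 hours but less than 21 days non-evaluable unless the cause was a DLT. The rule is written for cycles that are repeated, so its reach to a permanent stop is arguable. If applied, the subject leaves the DLT set and may be replaced under Section 4.2.1. The event is uncounted either way.
- **Restart.** Section 6.2.2.1 calls its criteria general guidelines, and Section 6.8 allows a restart after grade 3 CRS once it is grade 1 or lower and the sponsor has been consulted. Discontinuation is not absolute, although the exception to permanent discontinuation is worded for a DLT.
- **Earlier missed dose.** If one pembrolizumab dose was already missed for toxicity, another miss would trigger the catch-all.
- **Lists may differ by design.** Other stopping criteria, such as more than one seizure, are not separate DLT clauses. This does not explain why a milder event counts and a more severe one may not.
- **Timing.** Section 2.3 says AMG 330 toxicities appear shortly after dose increases. The uncovered days lie mostly after the first days of the last step, when CRS is less expected.

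A reader might infer that the decision to open cohort 2 rests on an undercounted DLT rate. The documents do not support that: an early permanent stop counts through the 70% clause. A reader might also infer that one such event turns 1/6 into 0/6. That is not established, because the subject may instead be non-evaluable, and 6 is only the minimum number per cohort. Nor is an uncovered window of 23 of 77 days (30%) realistic: it needs equal doses at every step, which contradicts the planned increases.

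**Conclusion.** The point holds as a minor gap in the DLT definition. Unless the grade 2 clause is read with a clock from CRS onset, a grade 3 event that is grade 2 by day 5 but not grade 1 by day 7 meets no CRS DLT clause, while a grade 2 event of more than 7 days does.

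The consequence is confined to events starting after about 70% of planned AMG 330 dose: roughly the last 6 to 13 infusion days in cohort 1 and 5 to 10 in cohort 2. There the subject is either evaluable without a DLT or non-evaluable. This rests on assumed step ratios of 1.25 to 3, a stop that is permanent, and no earlier missed pembrolizumab dose.

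The documents give no rate of slow resolution. Section 4.3 says the mitigation approach in the first-in-human study allows CRS to resolve within 7 days, so few such events are expected. The event would still appear in the adverse event tables of SAP Section 9.6.2.

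**What to change.** In the grade 3 CRS clause of Section 6.2.1, after the 5-day limit, add: *or to grade 1 or lower within 7 days of CRS onset*. In the grade 2 clause, state that its 7 days also run from CRS onset. The two grade 3 limits are already in Table 6-5; the onset clock is a new clarification.

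The cost is the wording of two clauses in one section. No new data, visits or subjects are needed, and SAP Section 5.4 follows automatically because it refers to Section 6.2.1. The downside is that the DLT count may be slightly higher.

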6.2.2 Dosage Adjustments, Delays, Rules for Withholding or Restarting, Permanent Discontinuation

6.2.2.1 Amgen Investigational Product: AMG 330

Subjects will be monitored continuously for adverse events while on study therapy.

Subjects will be instructed to notify their physician immediately for any and all adverse events. The criteria presented in this section for dose modifications and delays for AMG 330 are meant as general guidelines.

Criteria for Dose Delay or Dose Reduction

Subjects will receive continuous AMG 330 therapy as long as they have not had disease progression or an adverse event requiring dose modification, as described below.

Subjects who experience a grade 4 non-hematologic adverse event will not receive additional protocol-related therapy and will be removed from study unless discussed and agreed upon by the Sponsor and investigators that it is in the best interest of the subject to receive additional therapy with AMG 330 (eg, if the subject has demonstrated a response to therapy).

Dose modifications, interruptions, or delays may occur in the setting of lower grade adverse events based on the clinical judgement of the investigator, and in consultation

with the sponsor. Dose reductions should be to the previous lower dose level, or to a dose level in between the previous dose level and the current dose level, after discussion between the investigator and the sponsor.

No more than 2 dose level reductions of AMG 330 will be allowed per subject. If a third dose reduction is required, the subject must discontinue AMG 330 (and pembrolizumab, if receiving combination therapy based on response to therapy). Dose re-escalation after a dose reduction may occur in limited circumstances (such as a change in attribution of adverse event, or if re-escalation is in the best interest of the subject) after discussion and agreement between the sponsor and the investigator.

For an adverse event requiring dose modification, AMG 330 (and pembrolizumab for subjects receiving combination therapy) should be interrupted to allow recovery from the adverse event. Re-initiation of study drug cannot occur until adverse event decreases to grade ≤ 1 . In case of delayed recovery to grade ≤ 1 from treatment-related adverse events that results in a delay of treatment for > 21 days, the subject will not receive additional protocol-related therapy and will be removed from study unless discussed and agreed upon by the sponsor and investigators that it is in the best interest of the subject to receive additional therapy with AMG 330 and pembrolizumab (eg, if subject demonstrated response to therapy).

Assessment of causality (chronology, confounding factors such as disease, concomitant medications, diagnostic tests and previous experience with the agent) must be determined and documented by the investigator, prior to dose modification.

In case of grade 2 CRS, administration of AMG 330 can be continued on the currently tested dose level for 8 hours, and treatment provided to mitigate CRS symptoms. If symptoms do not improve to grade 1, the dose will be de-escalated by 50% for an additional 24 hours. If CRS grade 2 resolves to grade 1, the dose can be re-escalated back to the level being tested. If symptoms persist, AMG 330 infusion will be interrupted and pembrolizumab infusion will be delayed until symptoms improve to grade 1. If treatment is interrupted for < 24 hours, the interrupted AMG 330 dose can be resumed and re-escalated back to the tested dose level. If treatment is interrupted for > 24 hours, restart or repeat rules apply (see below).

In case of grade 3 CRS, AMG 330 treatment must be interrupted and pembrolizumab treatment postponed. Sponsor has to be consulted prior to a planned re-start. In case

of grade 4 CRS, treatment must be permanently discontinued. See [Section 6.8](#) for specific instructions for the management of CRS.

If the same grade 3 non-hematologic adverse event recurs despite a dose reduction, a second dose reduction versus discontinuation of the subject from further protocol therapy should be discussed and agreed upon the sponsor and investigators.

If a DLT occurs in a subject with clinical benefit from treatment, a restart at a lower dose can be considered if the toxicity has resolved to grade ≤ 1 and after consultation with the sponsor. If AMG 330 is discontinued, pembrolizumab may be continued as a monotherapy until disease progression for a maximum of 35 cycles (approximately 2 years) after discussion and agreement between the sponsor and the investigator. If pembrolizumab is discontinued, AMG 330 may be continued as a monotherapy.

Dose delay: treatment should be interrupted until the adverse event is resolved to grade ≤ 1 , and can then be resumed at the same dose unless the interruption lasted for more than 24 hours, please see below. (Note: if the event needs > 21 days to resolve, treatment has to be permanently discontinued, see also below).

Infusion Interruption

Significant events requiring a change in treatment will be managed by immediate infusion interruption:

- The subject experiences a DLT as defined in [Section 6.2.1](#)
- The subject experiences a clinically relevant grade 4 adverse event related to investigational product (see above) but does not meet the DLT criteria
- The subject meets criteria for discontinuation of investigational product as described in [Section 6.2.2](#)
- The subject experiences disease related adverse events and AMG 330 interruption is required for medical interventions
- Technical problem with the infusion pump
- The investigational product is incorrectly prepared or administered (eg, overdose)

Restarting the Infusion

Treatment may resume if the interruption is ≤ 21 days and if:

- The interruption occurred due to other reasons than toxicity (disease-related events, technical or logistic reasons; eg, diagnostic measurements). The infusion can be restarted at the same dose and without additional measures.
- The toxicity has resolved to CTCAE v5 grade ≤ 1 (in case of dose reduction, infusion may be re-started without prior resolution of the toxicity to CTCAE v5 grade ≤ 1 if the adverse event is not clinically relevant and upon discussion and agreement between the investigator and the sponsor)

Please also refer to specific guidance on restart after CRS in [Section 6.8](#). Restarting the infusion after a treatment interruption requires care. The re-start should be performed in the hospital, under supervision of the investigator or designee, if the reason for the interruption was other than a technical issue or the interruption exceeded 4 hours independent of reason. Assessments should be performed after infusion re-start depending on the length of the interruption. The subject should be hospitalized for at least 48 hours after re-start of the infusion.

In case of an AMG 330 infusion interruption of > 24 hours, regardless of the reason for interruption, re-start of the infusion (repeat cycle) should be performed using step doses, which will be defined upon consultation with the sponsor. Only 2 repeat cycles may be performed in cycle 1. For cycle 2 and beyond, additional repeat cycles can be permitted upon discussion and agreement between the investigator and sponsor.

Step doses will be performed within 1 – 2 weeks (\pm 1 day) to return to the interrupted AMG 330 dose level, and the number and duration of repeat step doses will depend on the level of interrupted AMG 330 dose. During this 1-2 weeks, [Table 1-7 Schedule of Activities](#) should be followed (eg, for AMG 330 doses interrupted at [REDACTED] μ g/day and below, 2 step doses can be used: [REDACTED] μ g/day for 3 days followed by [REDACTED] μ g/day for 4 days; for doses interrupted above [REDACTED] μ g/day, 3 step doses can be used: [REDACTED] μ g/day for 1 day followed by [REDACTED] μ g/day for 3 days followed by [REDACTED] μ g/day for 3 days). In case of AMG 330 infusion interruption for < 24 hours, regardless of the reason for interruption, restart of infusion should be performed at the same dose level as the last dose level. Administration of pembrolizumab will remain on the Q3W schedule.

After 2 unsuccessful restarts, the subject may remain on the study and continue AMG 330 treatment with a previously tested target dose that has been well tolerated. The dose of pembrolizumab will remain unchanged.

Dexamethasone (8 mg IV) should be administered within 1 hour prior to re-start and within 1 hour prior to each AMG 330 dose step(s). Dexamethasone is not required prior to the pembrolizumab administration unless it co-occurs with the AMG 330 step dose. In cases when administration of pembrolizumab co-occurs with AMG 330 step, pembrolizumab is administered first followed by dexamethasone followed by AMG 330. The subject should be hospitalized starting from re-start of infusion until 72 hours after the dose step. After each dose level increase, vital signs will be obtained as per the Schedule of Activities (see [Table 1-1](#), [Table 1-3](#), [Table 1-5](#)).

The number of days of exposure to both investigational products before and after an interruption should sum up to at least 70% of planned cumulative dose of AMG 330. In this case, the subject would still be DLT-evaluable. However, if the cycle was interrupted for more than 24 hours but less than 21 days, a new repeat cycle should be started and the interrupted cycle would not be evaluable for DLT, unless the event that lead to the interruption was a DLT.

Note: The end of infusion bone marrow assessment should be performed once it is confirmed that the cycle will not be resumed to assess treatment response. [REDACTED]

[REDACTED]

[REDACTED].

Permanent Discontinuation

A subject will permanently discontinue treatment with investigational product in the event of:

- Dose-limiting or other unmanageable toxicity. Exception: If a DLT occurs in a subject with a clear clinical benefit from treatment a restart at a lower dose can be considered if the toxicity has resolved and after consultation with the sponsor. This includes:
 - Grade 4 CRS
 - Grade 3 CRS occurring at the initial step dose for a cycle (ie, at the 10 µg/day)
 - Grade 2 or 3 CRS meeting any of the criteria listed below:
 - Grade 2 or 3 CRS that does not improve to ≤ grade 1 within 7 days
 - Grade 3 CRS that does not improve to ≤ grade 2 within 5 days
- Re-occurrence of the same grade 4 adverse event
- 3 infusion interruptions > 24 hours in cycle 1
- Disease progression as defined by 2017 European LeukemiaNet (ELN) criteria ([Döhner et al, 2017](#))
- Withdrawal of subject's consent to treatment
- Subject or investigator not compliant with the study protocol
- Occurrence or progression of a medical condition which in the opinion of the investigator should preclude further participation of the subject in the study
- Hematological or extramedullary relapse subsequent to CR/CRh*/CRI/MLFS on protocol treatment. Exception: a blast count > 5% at the pre-dose assessment (after the infusion-free interval) would not lead to permanent treatment discontinuation even if the count had been < 5% directly after the previous treatment cycle.
- An infusion interruption of more than 21 days due to an adverse event not clearly related to the underlying disease.

- Occurrence of CNS-related adverse event considered related to AMG 330 by the investigator and meeting 1 or more of the following criteria:
 - More than 1 seizure
 - A CNS-related adverse event CTCAE grade 4
 - A CNS-related adverse event leading to treatment interruption that needed more than 1 week to resolve to CTCAE grade ≤ 1
- Non-manageable GVHD
- Investigator's decision that a change of therapy is in the subject's best interest
- Administration of relevant non-permitted concomitant medications

Women who become pregnant while on study through 1 week after receiving the last dose of study drug will not receive subsequent scheduled doses and will be followed for safety until the end of study visit.

Men with pregnant partners or whose partners become pregnant while the subject is on study will receive subsequent scheduled doses and must practice sexual abstinence or use a condom while on study through 120 days after receiving the last dose of study drug.

All reasons for treatment discontinuation should be clearly and concisely documented in the eCRF. If a subject has not continued to present for study visits, the investigator should determine the reason and circumstances as completely and accurately as possible.

In any case of premature treatment discontinuation, the investigator should make every effort to perform all examinations scheduled for the end of treatment and safety follow-up visits. These data should be recorded, as they comprise an essential evaluation that should be performed prior to discharging any subject from the study and to allow for the evaluation of the study endpoints.

